#### **5.2 Treatment Regimen**

It is important to uptitrate and downtitrate the dose of baclofen to minimize side-effects. We will parallel the titration schedule used by Franklin et al (2009) in their study of 20 mg of baclofen given four times per day. In the latter study, baclofen was well tolerated without significant differences between baclofen and placebo groups—for the chief side-effect of sedation, the baclofen group had 20 mild, 4 moderate and 0 severe reports of sedation compared to 4 reports of mild sedation and 0 reports of either moderate or severe sedation with placebo (Franklin et al, 2009). Our titration schedule for the 90 mg/d dose is shown in Table 1. The 30 mg/d arm will reach 30 mg/d at day 3 and titrate down starting at day 101.

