**Table 1: Baclofen Titration and Dosing Schedule**

Day	Morning Dose	Afternoon Dose	Bedtime Dose	Total Daily Dose
1-2	placebo	10 mg	10 mg	20 mg
3-4	10 mg	10 mg	10 mg	30 mg
5-6	10 mg	10 mg	20 mg	40 mg
7-9	20 mg	20 mg	20 mg	60 mg
10-11	20 mg	20 mg	30 mg	70 mg
12-94	30 mg	30 mg	30 mg	90 mg
95-97	20 mg	20 mg	30 mg	70 mg
98-100	10 mg	20 mg	20 mg	50 mg
101-103	placebo	10 mg	20 mg	30 mg
104-106	placebo	placebo	10 mg	10 mg
107	placebo	placebo	placebo	0 mg

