Individuals who appear eligible, as determined by the investigative team, will be scheduled to come to the UNC Hospitals for more comprehensive screening. Prior to full screening, individuals will read and sign the informed consent and be given a copy for their records. A breathalyzer test using an Alco-Sensor III breathalyzer machine (Intoximeters, Inc., St. Louis, MO) will be administered (must be 0.00 gms/dl to give informed consent). Height and weight will be measured and BMI calculated. Medical personnel will conduct a medical history and examination including a neurological examination. Over-the-counter and prescription medication use will be recorded. The Fagerstrom Test for Nicotine Dependence (Heatherton et al, 1991) will be administered to smokers. Laboratory evaluations will include complete blood count (CBC) with differential; chemistries including bilirubin, AST, ALT, Alkaline Phosphatase, GGT, sodium, potassium, chloride, blood urea nitrogen, creatinine, and glucose; and urinalysis and urine toxicology. A carbohydrate deficient transferrin (CDT) sample will be drawn. CDT samples will be stored frozen and then shipped in batches of 40 to [name] lab in Charleston, South Carolina for assay. With subjects' permission a sample of blood will also be obtained to archive for possible future genetic analyses. Women will be given a urine pregnancy test (Ub-HCG) at screening and at weeks 4, 8, 12 and 16. Trained interviewers will conduct the psychiatric screening interview using the M.I.N.I. (Sheehan et al., 1999) and the SCID Substance Use Disorders Module to establish DSM-IV criteria for alcohol dependence and to assess for other substance use disorders (First, 2002). The study coordinator will conduct the pretreatment 90-day Timeline Followback interview (TLFB, Sobell et al, 1988) and potential participants will complete the Spielberger State/Trait Anxiety Inventory (SSTAI) (Spielberger et al (1969)), the Drinker's Inventory of Consequences (DrInC, Miller et al, 1995) the FHAM to assess family history of alcohol problems (Rice et al, 1995), the University of Rhode Island Change Assessment Scale (URICA, McConaughy et al, 1989) to assess motivation level, the Penn Alcohol Craving Scale (PACS, Flannery et al 1999) to assess craving, and the Insomnia Severity Index (Bastien et al, 2001) to assess sleep problems. Additionally, potential participants will fill out a short evaluation of their treatment goals. This visit should take about 3 hours.

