**Primary Efficacy Analysis:** For the Summary measure, we will fit a general linear model on the outcome variable, consisting of main effect for treatment status. Goodness-of-fit, will be analyzed for outliers and influential observations. While these summary measure approaches are simple to implement and commonly used, information concerning the effect of time on the treatment effect is ignored. To understand the impact of time we will also conduct a repeated measures models analysis. From the weekly usage measures we will fit a mixed effects model consisting of main effect for treatment status. This repeated measures approach provides more information about the effect of treatment over time and therefore, more power compared to summary analyses above. We will also include the interaction of time and treatment. The interaction of time and treatment will answer the question as to whether the treatment effect is consistent over the entire treatment period or varies over the weeks. The mixed effects framework offers flexibility for the outcomes, e.g. any usage versus none, or count outcome data, e.g. number of abstinent days (Wolfinger and O'Connell, 1993). Appropriate covariance structure will be determined based on the AIC (Akaike Information Criteria) and BIC (Bayesian Information Criteria). We will evaluate the baclofen effect for changes in CDT using the mixed model approach described above. Within all framework, statistical contrasts will allow us to compare the two levels of BAC to PBO, as well as statistically contrasting the two levels of BAC. The advantage of the statistical contrasts is it allows us to use all available data to estimate the variance (variance-covariance for the repeated measures) of the outcome, while also properly distributing the degrees of freedom for the analytical test to account for the three levels of treatment.

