## **10 Study Monitoring, Auditing, and Inspecting**

### **10.1 Study Monitoring Plan**

The investigator will allocate adequate time for such monitoring activities. The Investigator will also ensure that the monitor or other compliance or quality assurance reviewer is given access to all the above noted study-related documents and study related facilities (e.g. pharmacy, diagnostic laboratory, etc.), and has adequate space to conduct the monitoring visit.

We will follow our standard protocol for monitoring of clinical trials. First, subjects are screened to exclude those who might have an increased risk associated with study participation, e.g. renal failure, diabetes mellitus, pregnancy. Pregnancy will be initially screened using a blood test with increased sensitivity compared to urine tests. Second, subjects are monitored on a regular basis with visits at post-randomization weeks 1, 2, 3, 4, 6, 8, 10, 12, 14 and 16. At these visits vital signs are taken and subjects are asked about any side-effects or problems that they are having. At weeks 4, 8, 12 and at termination a liver profile and creatinine level are examined. Participants with elevated creatinine or AST/ALT levels  $> 5X$  ULN or a bilirubin  $> 1.5$  ULN will have their medication tapered and stopped and will be monitored by study physicians. In these instances another liver profile and creatinine will be drawn within 2-4 weeks.

Participants will be contacted by telephone 4 weeks after the final trial visit to ascertain drinking behavior and any physical or psychiatric problems. Individuals with clinically significant problems will be referred for appropriate psychiatric or medical treatment.

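### The only post-baseline CDT sample is drawn after the taper, so the one biomarker with a planned efficacy analysis gives no clean on-treatment comparison

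*Combined protocol and SAP*

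**What the plan says.** Section 7.2 (Primary Efficacy Analysis) gives CDT one sentence: "We will evaluate the baclofen effect for changes in CDT using the mixed model approach described above". The model it points to is the one for drinking: "From the weekly usage measures we will fit a mixed effects model consisting of main effect for treatment status". That model also has a time-by-treatment interaction, meant to show whether the effect changes from week to week, and a covariance structure chosen by AIC and BIC. In every model, contrasts compare each dose with placebo and the two doses with each other. GGT is named beside CDT in Section 3.1 but has no analysis in Section 7.2.

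For sampling, Section 6 describes the screening visit: "A carbohydrate deficient transferrin (CDT) sample will be drawn". The schedule of assessments in Section 6 marks CDT at screening and at week 16, with nothing between. Section 10.1 counts visits from randomisation: "visits at post-randomization weeks 1, 2, 3, 4, 6, 8, 10, 12, 14 and 16".

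For dosing, Section 5.2 refers to "Table 1: Baclofen Titration and Dosing Schedule" for the 90 mg/d arm. Its full-dose row is "12-94 30 mg 30 mg 30 mg 90 mg", its last active row is "104-106 placebo placebo 10 mg 10 mg", and day 107 is placebo only. For the other active arm, Section 5.2 says: "The 30 mg/d arm will reach 30 mg/d at day 3 and titrate down starting at day 101". The day of that arm's last active dose is not stated.

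**The concern.** The drinking outcomes are self-reported through the Timeline Followback interview (TLFB). A biological marker is useful here because it can support or question those reports, but only if the sample reflects drinking while participants were taking the doses being compared. The one follow-up sample is scheduled after the high-dose arm has come down through the other arm's dose and then stopped. If the interview data showed an effect and CDT did not, nobody could say whether the reports were inflated or the effect had faded with the drug.

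The named method is a second difficulty. A model built for weekly series, with a time course and a covariance search, is assigned to a marker with one post-baseline value.

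**Working it through.** The plan gives no effect size, SD or power for CDT, so there is no stated figure to reproduce. The check is a day count, a look-back count and a model comparison.

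**1. Day of the sample.** If the initial visit is day 0, week 16 is 16 × 7 = day 112. If it is day 1, week 16 is day 113. Both are carried through.

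**2. Distance from dosing.**

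| Reference day (source) | Arm | Days to week 16 |
|---|---|---|
| 94, last 90 mg day (dosing table) | 90 mg/d | 112 − 94 = 18; 113 − 94 = 19 |
| 106, last active dose (dosing table) | 90 mg/d | 112 − 106 = 6; 113 − 106 = 7 |
| 100, last full-dose day (taper starts day 101, Section 5.2) | 30 mg/d | 112 − 100 = 12; 113 − 100 = 13 |

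From day 101 the 90 mg/d arm is itself scheduled to receive 30 mg or less (30, then 10, then 0). That covers the last 112 − 101 = 11 to 113 − 101 = 12 days before the sample, which is why the contrast between doses is the most exposed. Section 7.1 bases power on drinking summaries over 12 weeks; this sample comes 16 − 12 = 4 weeks after that point.

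**3. What the sample could reflect.** The documents do not say how many days of drinking CDT represents. The windows below are assumptions, counted for the 90 mg/d arm over the days before the sample.

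| Assumed window | Days on any active dose | Days at 90 mg |
|---|---|---|
| 14 days | 8–9 | 0 |
| 21 days | 15–16 | 3–4 |
| 28 days | 22–23 | 10–11 |

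For example, a 28-day window before day 112 runs from day 84 to day 111. Active days are 84 to 106, so 23; days at 90 mg are 84 to 94, so 11.

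A week 12 sample falls on day 84 or 85. Its 28-day window starts no earlier than 84 − 28 = day 56, inside the full-dose period of days 12 to 94. All 28 days are then scheduled at 90 mg.

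**4. What the model becomes.** Each participant has two CDT values, hence one change.

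- If the change is the response, there is one record per participant and the model is an ordinary linear model.
- If both values are responses, the treatment effect is the group-by-time term, which then means change from screening rather than consistency over weeks.

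Both were fitted to one simulated data set (120 participants, three arms, complete data). The group-by-time estimates from the random-intercept model were −0.260 and −0.358, each with SE 0.202. The change-score model gave −0.260 and −0.358, each with SE 0.202. The analysis is estimable, but it offers no time course and AIC and BIC have nothing useful to choose between.

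**5. Missing values.** Section 6 (Subsequent Treatment Visits) does not list CDT at early termination, and the schedule footnote does not settle it. If dropouts give no sample, about 0.162 × 120 = 19 participants (the attrition in Section 7.1) to 0.25 × 120 = 30 (the 75% retention target) would have no post-baseline CDT.

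**The case against.** The best defence is that CDT is a supportive measure. It is in no objective in Section 2 and no power calculation in Section 7.1, and Aim 1 rests on percentages of abstinent and heavy drinking days. This stands, and it limits the weight of the point. It does not explain why the one biomarker given an analysis is sampled only after the taper.

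Several stronger readings are tempting, and the documents do not support them:

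- *CDT cannot show an on-treatment effect.* This depends on a look-back window that the documents do not give. Under the longer assumed windows most of the days covered are on active drug, though often at a reduced dose.
- *A positive CDT result could not be tied to treatment.* The arms are randomised and placebo-controlled, so a difference at week 16 is attributable to assignment, including any persisting effect. Late timing dilutes an effect and clouds a null result; it does not remove attribution.
- *The mixed model cannot be used.* It can be fitted, as shown above; it simply adds nothing to a change-score analysis when data are complete.
- *CDT is the trial's only objective marker of drinking.* GGT is in the schedule's blood panel at weeks 4, 8, 12 and 16, and the first three fall at full dose. What it lacks is an analysis.
- *Every arm has been off drug since day 107.* The table is for the 90 mg/d arm, and the last active day of the 30 mg/d arm is not stated.

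**Conclusion.** The point holds in a limited form. As scheduled, no CDT value is taken during maintenance, and the only follow-up value is an end-of-study, post-taper measure rather than a clean on-treatment one. The likely harm is a diluted effect, worst for 90 versus 30 mg/d, and a null result that cannot be interpreted. The amount of dilution cannot be calculated, because the plan gives neither a CDT window nor an expected CDT effect.

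The day counts assume visits on their nominal weeks and dosing as tabulated. The equality of the two models assumes complete data. The TLFB conclusions do not change. This is a cheap improvement, not a threat to the main analysis.

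**What to change.** 1. Take the post-baseline CDT sample at a maintenance-phase blood draw that is already planned. The schedule, Section 8.1 (Abnormal Laboratory Values) and Section 10.1 place draws at weeks 4, 8 and 12, whereas Section 6 (Subsequent Treatment Visits) says weeks 4 and 10. These passages must be reconciled first. Weeks 10 and 12 both fall within days 12 to 94, so the change works either way.
2. Choose between moving the week 16 tube, which adds no assay but loses the end-of-study value, and adding a tube, which costs one extra assay per participant. A week 12 sample leaves out the last 94 − 85 = 9 to 94 − 84 = 10 days at 90 mg.
3. In Section 7.2, replace the CDT sentence with a linear model of on-treatment CDT on treatment group, adjusted for screening CDT, with the same three contrasts. Label any week 16 CDT as an end-of-study, post-taper measure.
4. Give GGT the repeated-measures analysis, using its on-treatment values and the screening value. No new sampling is needed under the present schedule.
5. State whether CDT is drawn at early termination.

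The cost is wording in the schedule, the laboratory instructions and Section 7.2, plus the extra assay if a tube is added.

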## 7 Statistical Plan

### 7.1 Sample Size Determination

Aim 1. Our power calculations are based on the summary scores over the 12 weeks of treatment (%HDD and %ABST). Under our modified design, we must consider our 3 group design. We use Cohen's (1988) effect size definition for standardized difference for our continuous outcomes, coupled with the work of Addolorato et al. (2011) as guidelines for our power estimates and anticipated effect sizes. The Addolorato et al. (2011), similar to our design consists of 2 medication groups and a PBO reference reports contrast of incidence rates between the medication arms and PBO. Thresholds of the size of the contrasts, for comparability to the Cohen guidelines, are as defined by Rosenthal (1996) who parallels Cohen's (1988) terminology of small, medium, and larger effects for qualitative indexes such as Odds ratios and Incidence rates. Addolorato et al. (2011) saw a small to medium effect size for the contrast between PBO and 30mg. Similarly they saw a medium to large effect for the contrast between PBO and 60mg. Replicating a small effect size(Cohen's  $d=0.2$  for our outcomes) for the contrast between PBO and 30mg coupled with a large effect size (Cohen's  $d=0.8$  for our outcomes) for the contrast between PBO and 90mg, provides 82.2% power with 120 participants (40/arm) in testing the overall baclofen effect as well as 84.7% power to contrast 30 mg to 90 mg under the assumed effect sizes. We assume seeing a large effect size for the PBO-90mg is reasonable due to the medium-large effect seen by Addolorato et al. (2011) 60mg-PBO contrast. Interpreting the effect size for our outcomes, the PBO-overall medication contrast corresponds to a difference of 12% in %HD/%ABS rate between PBO and pooled medication sample over the 12 week period under an arc-sine transformation of the observed individual rates. The effect sizes for the contrast between medication arms corresponds to a difference of 19% in %HD/%ABS rates. We experienced 16.2% attrition in Garbutt et al (2010); therefore, a slightly larger effect size would be required to provide sufficient power for the overall BAC effect. Assuming an average effect size of 0.55, corresponds to a difference of 13% in %HDD/%ABS rate between BAC and PBO, we will have power of 82.0% to detect a statistically significant baclofen effect while accounting for attrition and 78.1% power to detect a significant difference between medication levels at the 0.6 effect size accounting for attrition.

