
For Aim 2, our main interest is the moderation effect of pre-treatment drinking rates on the BAC effect during treatment, for which we have some evidence as indicated in our Figure 1. Power calculations of a significant DDD x treatment interaction were implemented through SAS power procedure PROC GLMPOWER. Power derivations depended on an expected effect size, where based on the Addolorato et al. (2002) finding in a sample consisting of more DDD pre-treatment, we expect a large effect for BAC compared to PBO for those(Cohen's  $d > 1$ ), whereas Garbutt et al. (2010) in a sample consisting of lower DDD pre-treatment, found no difference (Cohen's  $d=0$ ). The pattern of this behavior is consistent with Figure 1 where more separation between BAC and PBO is evident in those with higher pre-treatment DDD. To detect this interactive behavior in our proposed design, where we assume an effect size of 1.2 corresponding to a difference of 28% in %HDD/%ABS rates in the Heavy Drinking group, and an effect size of 0 within the non-Heavy drinking group, the study will have 86.7% power to detect a significant interaction between Heavy drinking and BAC assignment. Accounting for 16.2% attrition provides 80.2% power to detect the same effect. Power calculations for the moderation assume 40 per treatment arm, with pre-treatment heavy drinking balanced per arm (20 low and 20 high).

For Aim 3, power is comparable to Aim 1, where we will have 82.2% power to detect a BAC effect for anxiety or an effect size of 0.5 and 82.0% power to detect an effect size of 0.55 while accounting for 16.2% attrition.

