## 7.2 Statistical Methods

**Specific Aim 1. To test the hypothesis that baclofen, 30 mg/d and 90 mg/d, is well tolerated and superior to placebo in enhancing abstinence and reducing heavy drinking days in alcohol dependence and that 90 mg/d is superior to 30 mg/d.**

Summary measures of the proportion of abstinence days/heavy drinking days will be derived from the TLFB for the entire medication period. We will derive weekly drinking measures from TLFB as well to provide information on the impact of time on usage. Descriptive statistics and exploratory graphing will be used to assess the distribution of the data and the need for transformations. In the case of %ABS/%HDD, the arc-sine transformation is quite commonly used.

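### Aim 1 has two unranked outcomes, three or four contrasts and two models under one primary heading, with no alpha, sidedness, deciding test or multiplicity rule

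*Combined protocol and SAP*

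**What the plan says.** Specific Aim 1 in section 7.2 covers tolerability and puts forward the hypothesis that baclofen at both doses is "superior to placebo in enhancing abstinence and reducing heavy drinking days in alcohol dependence and that 90 mg/d is superior to 30 mg/d". That gives two drinking outcomes, neither ranked first. Section 7.1 likewise powers both summary scores together.

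The paragraph headed *Primary Efficacy Analysis* first describes a general linear model on the whole-period summary measure. It then says "To understand the impact of time we will also conduct a repeated measures models analysis", which is a mixed model on weekly data with a time-by-treatment term. Across these frameworks, "statistical contrasts will allow us to compare the two levels of BAC to PBO", and the two doses are compared with each other. That is three contrasts. A fourth, pooled baclofen versus placebo, carries the sample size in section 7.1 but is missing from the list of contrasts in 7.2.

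The power statement is that the design "provides 82.2% power with 120 participants (40/arm) in testing the overall baclofen effect as well as 84.7% power" for 30 mg versus 90 mg. After dropout, "we will have power of 82.0% to detect a statistically significant baclofen effect while accounting for attrition". Neither section states a significance level, one- or two-sided testing, an order of tests or an adjustment. The remark in 7.2 about degrees of freedom and three treatment levels concerns variance estimation within a model; it does not limit the error rate across tests.

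**The concern.** Two outcomes, three contrasts and one model make 2 × 3 × 1 = 6 tests. Two outcomes, four contrasts and two models make 2 × 4 × 2 = 16. The plan does not say which of them decides Aim 1. If the result can be taken from whichever test is significant, the error rate of the primary aim is well above that of a single test, and a reader of the report could not tell how much.

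This matters in this field. Section 1.4 describes placebo-controlled trials that disagree. It also describes a dose-comparison pilot with no effect on heavy drinking or abstinent days, whose positive finding came from a secondary analysis. A result that depends on which outcome, contrast or model is emphasised would not resolve that disagreement.

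**Working it through.** **1. What level does the plan use?** None is stated, so I inferred it from the power figures.

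Inputs from section 7.1: 40 per arm; "Replicating a small effect size(Cohen's $d=0.2$ for our outcomes") for 30 mg versus placebo, "coupled with a large effect size (Cohen's $d=0.8$ for our outcomes") for 90 mg versus placebo. Hence pooled versus placebo is (0.2 + 0.8)/2 = 0.5, and 90 versus 30 mg is 0.8 − 0.2 = 0.6. Residual df = 120 − 3 = 117; critical t is 1.658 (one-sided 0.05) or 1.980 (two-sided 0.05). Power comes from the noncentral t with noncentrality d / √(1/n₁ + 1/n₂).

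| Contrast | Noncentrality | One-sided 0.05 | Two-sided 0.05 | Plan |
|---|---|---|---|---|
| Pooled vs placebo | 0.5/√(1/80 + 1/40) = 2.582 | 82.2% | 72.6% | 82.2% |
| 90 vs 30 mg | 0.6/√(1/40 + 1/40) = 2.683 | 84.7% | 75.8% | 84.7% |

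With 16.2% dropout, 40 × 0.838 = 33.5, so 33 per arm. Pooled at d = 0.55 gives 0.55/√(1/66 + 1/33) = 2.580, with power 82.0% one-sided (the plan's figure) and 72.4% two-sided.

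Aim 2 behaves differently. The plan says "the study will have 86.7% power to detect a significant interaction between Heavy drinking and BAC assignment". With pooled baclofen and d = 1.2 against 0, the standard error is √(1/40 + 1/20 + 1/40 + 1/20) = 0.387 and the noncentrality 1.2/0.387 = 3.10. Two-sided 0.05 gives 86.7%; one-sided gives 92.4%. So Aim 1 reproduces only at one-sided 0.05 and Aim 2 only at two-sided 0.05. The level of 0.05 is an inference, and the sidedness differs between aims.

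**2. Chance of at least one significant test when nothing works.** I used simulation under the global null with three arms of 40. Each contrast is t = Σcₐȳₐ / (s√(Σcₐ²/40)) on 117 df, every test is at 0.05, and both outcomes are oriented so that positive is favourable.

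Correlations between contrasts follow from the shared arms; for example, the two dose-versus-placebo contrasts correlate at 0.5. Two correlations are not in the documents and are assumed: 0.5-0.9 between outcomes (in absolute value) and 0.9 between the two models.

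| What is counted | Lowest: 3 contrasts, summary model, outcomes 0.9 | Highest: 4 contrasts, both models, outcomes 0.5 | Single test |
|---|---|---|---|
| Two-sided 0.05, either direction | 16.6% | 29.1% | 5% |
| One-sided 0.05, favourable | 16.7% | 27.9% | 5% |
| Two-sided 0.05, favourable only | 9.0% | 16.1% | 2.5% |

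For two-sided tests in either direction, by model:
- Summary model alone: 16.6% to 22.0%.
- Both models: 22.2% to 29.1%.

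**3. Sensitivity (two-sided, either direction).**
- Outcomes perfectly correlated, three contrasts, one model: 12.3%.
- Outcomes uncorrelated, four contrasts, two models correlated 0.7: 36.2%.
- One outcome and one model: 12.2% with three contrasts, 12.8% with four.
- The three placebo contrasts only, one model, outcome correlation 0.5-0.9: 13.4-17.0%. Counting favourable results only, this is 6.7-8.6%.

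The time-by-treatment term, the optional transformation and the baseline-driven covariates in 7.2 were not counted.

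**4. Which contrast should come first?** Under the plan's own effects, 90 mg versus placebo has noncentrality 0.8/√(1/40 + 1/40) = 3.578 and 94% power at two-sided 0.05. If pooled baclofen came first (72.6%), about 22% of trials would have a significant 90 mg result that could not be claimed. Both contrasts are significant in 72.4% of trials, so testing 90 mg first costs the pooled contrast only 72.6 − 72.4 = 0.2 points.

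**The case against.** Four points on the other side have force.

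- **The rule that any one result suffices is not the plan's.** Aim 1 joins its hypotheses with *and*. If every component had to be significant, error would not be inflated at all. This stands: the inflation is conditional on how success is read. But the plan adopts neither rule, and its power is given contrast by contrast, not for all jointly.
- **The summary model is arguably already the main one.** It comes first, section 7.1 bases power on it, and the mixed model is introduced as an addition for studying time. This largely stands, and a reader who infers that neither model has any priority goes too far. Still, both sit under the primary heading, 7.2 describes the mixed model as the more powerful, and no rule says which prevails. The summary model alone still gives about 17-22%.
- **The treatment main effect could be seen as a gate for the contrasts.** The plan does not say that contrasts are tested only after a significant overall test, nor that this would cover both outcomes.
- **This is Phase II.** That tempers the consequences. The Abstract speaks of goals towards determining baclofen's clinical value, not of settling it. A reader might infer that the trial cannot support its own claim; the documents do not go that far. Aim 1 is nonetheless framed as superiority, so it needs a stated deciding test.

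A reader might also infer that the plan carries a 16-29% risk of a false efficacy claim where 5% was intended. The documents do not support that as a flat statement. They give no alpha or sidedness. At two-sided 0.05 that range also counts placebo beating baclofen and 30 mg beating 90 mg.

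**Conclusion.** The gap is real and should be closed: Aim 1 has 6 to 16 candidate tests and no alpha, sidedness, deciding test or multiplicity rule. The size depends on a reading the plan does not fix. If each test is at 0.05 and any one significant result counts, the rate is about three to six times that of a single test under every direction rule examined, within the assumed correlations (from 16.6/5 = 3.3 to 16.1/2.5 = 6.4). Which of the three ranges applies turns on sidedness, and the plan's own figures point both ways: one-sided for Aim 1, two-sided for Aim 2. More extreme correlations widen the two-sided, either-direction range to about 12-36%. If success required every component of Aim 1, this inflation would not arise, but other power figures would then be needed.

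**What to change.** In section 7.2, before unblinding:

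1. Name one primary outcome and make the other a key secondary outcome.
2. Make the summary linear model, on which the power rests, the primary model and the weekly mixed model supportive.
3. State alpha and sidedness, and use the same convention in 7.1.
4. List the pooled contrast in 7.2 if it is to be tested, and fix one order. For example: 90 mg versus placebo, pooled baclofen versus placebo, 90 versus 30 mg, 30 mg versus placebo, stopping at the first non-significant step. Another order is acceptable if fixed in advance. Putting pooled baclofen first carries the 22% cost shown above.

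Cost: the change needs wording only, with no new data or participants. Contrasts after a failed step cannot be claimed. If two-sided 0.05 is chosen, section 7.1 must be restated: pooled versus placebo 72.6% rather than 82.2%, and 90 versus 30 mg 75.8% rather than 84.7%, before attrition and before any loss from the testing order.
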